4.5.4 Criteria to Resume Treatment

Subjects may resume treatment with study drug when the drug-related AE(s) resolve to Grade \leq 1 or baseline value, with the following exceptions:

- Subjects may resume treatment in the presence of Grade 2 fatigue.
- Subjects with baseline Grade 1 AST/ALT or total bilirubin who require dose delays for reasons other than a 2-grade shift in AST/ALT or total bilirubin may resume treatment in the presence of Grade 2 AST/ALT OR total bilirubin. Subjects with combined Grade 2 AST/ALT AND total bilirubin values meeting discontinuation parameters (Section 4.5.5) should have treatment permanently discontinued.
- Drug-related pulmonary toxicity, diarrhea, or colitis must have resolved to baseline before treatment is resumed.
- Drug-related endocrinopathies adequately controlled with only physiologic hormone replacement or glucose controlling agents may resume treatment.

If the criteria to resume treatment are met, the subject should restart treatment at the next scheduled timepoint per protocol. However, if the treatment is delayed past the scheduled timepoint per protocol, the scheduled study treatment administration will be delayed, but not skipped, until dosing resumes. In particular, this is to ensure that subjects in Arm N-I will receive 4 administrations of combined nivolumab and ipilimumab treatment if toxicity allows.

If dose delay is necessary for subjects in Arm N-I during Week 1-12, both nivolumab and ipilimumab must be delayed until treatment can resume. However, if a nivolumab-related infusion reaction prevents subsequent infusion of ipilimumab on the same day, the dose of ipilimumab should be replaced as soon as possible. In such instances, at least 19 days must elapse between the replacement dose of ipilimumab and the administration of the next dose of nivolumab combined with ipilimumab.

If treatment is delayed $>$ 6 weeks from the last dose, the subject must be permanently discontinued from study therapy, except as specified in Section 4.5.5.

Cobimetinib will be resumed in accordance with the Prescribing Information for Cotellic and dose modification summary provided in [Section 4.5.3](#).

4.5.5 Discontinuation Criteria

Nivolumab and Ipilimumab

Discontinuation criteria apply for all drug-related adverse events attributed to nivolumab, ipilimumab, or both.

Treatment should be permanently discontinued for the following:

- Any Grade 2 drug-related uveitis, eye pain, or blurred vision that does not respond to topical therapy and does not improve to Grade 1 severity within the re-treatment period OR requires systemic treatment.

- Any Grade 3 non-skin, drug-related adverse event lasting > 7 days, with the following exceptions for drug-related laboratory abnormalities, uveitis, pneumonitis, bronchospasm, diarrhea, colitis, neurologic toxicity, hypersensitivity reactions, and infusion reactions:
 - Grade 3 drug-related uveitis, pneumonitis, bronchospasm, diarrhea, colitis, neurologic toxicity, hypersensitivity reaction, or infusion reaction of any duration requires discontinuation
 - For Grade 3 endocrinopathy adverse events such as adrenal insufficiency, ACTH deficiency, hyper- or hypothyroidosis, or glucose intolerance, which resolve or are adequately controlled with physiologic hormone replacement (steroids, thyroid hormones) or glucose controlling agents, respectively, do not require treatment discontinuation
 - Grade 3 drug-related laboratory abnormalities do not require treatment discontinuation except:
 - ◆ Grade 3 drug-related thrombocytopenia > 7 days or associated with bleeding requires discontinuation
 - ◆ Any drug-related liver function test (LFT) abnormality that meets the following criteria require discontinuation:
 - AST or ALT > 8 x ULN
 - Total bilirubin > 5 x ULN
 - Concurrent AST or ALT > 3 x ULN and total bilirubin > 2 x ULN
- Any Grade 4 drug-related adverse event or laboratory abnormality, except for the following events which do not require discontinuation:
 - Grade 4 amylase or lipase abnormalities that are not associated with symptoms or clinical manifestations, or radiographic signs of pancreatitis. Consult with the BMS Medical Monitor for Grade 4 amylase or lipase abnormalities.
 - Isolated Grade 4 electrolyte imbalances/abnormalities that are not associated with clinical sequelae and are corrected with supplementation/appropriate management within 72 hours of their onset.
 - For Grade 4 endocrinopathy adverse events such as adrenal insufficiency, ACTH deficiency, hyper- or hypothyroidosis, or glucose intolerance, which resolve or are adequately controlled with physiologic hormone replacement (steroids, thyroid hormones) or glucose controlling agents, respectively, retreatment can be considered after discussion with the BMS Medical Monitor.
 - Grade 4 lymphocytopenia not associated with symptoms or clinical manifestations. It is recommended to consult with the BMS Medical Monitor for Grade 4 lymphocytopenia before treatment continuation.

- Any dosing interruption lasting > 6 weeks with the following exceptions:
 - Dosing interruptions to allow for prolonged steroid tapers to manage drug-related adverse events are allowed. Prior to re-initiating treatment in a subject with a dosing interruption lasting > 6 weeks, the BMS medical monitor must be consulted. Tumor assessments should continue as per protocol even if dosing is interrupted.
 - Dosing interruptions > 6 weeks that occur for non-drug-related reasons may be allowed if approved by the BMS medical monitor. Prior to re-initiating treatment in a subject with a dosing interruption lasting > 6 weeks, the BMS medical monitor must be consulted. Tumor assessments should continue as per protocol even if dosing is interrupted.
- Any adverse event, laboratory abnormality, or concurrent illness which, in the judgment of the Investigator, presents a substantial clinical risk to the subject with continued nivolumab, ipilimumab, or cobimetinib dosing.

If a subject in Arm N-I meets criteria for discontinuation of nivolumab, the subject should discontinue both nivolumab and ipilimumab and be taken off the treatment phase of the study entirely. However, if the investigator assesses the drug-related AE to be related to ipilimumab only and not related to nivolumab, ipilimumab dosing alone may be discontinued while nivolumab dosing is delayed until the subject meets criteria to resume nivolumab treatment (specified in [Section 4.5.4](#)). Nivolumab would be continued at 3 mg/kg with an every 2 week dosing interval. The relationship to ipilimumab should be well documented in the source documents and the BMS medical monitor needs to be contacted prior to continuation with nivolumab therapy.

Cobimetinib

Discontinuation criteria for cobimetinib are specified in [Section 4.5.3](#) and in the Prescribing Information.⁵⁷

For subjects on Arm N-I dose level 2d, if the investigator assesses drug related AEs to be related to ipilimumab or cobimetinib only and not related to other study drugs, treatment with the agent causing the AE alone may be permanently discontinued and treatment with the remaining drugs will continue. Treatment with the remaining drugs may only be resumed when the subject meets criteria to resume treatment according to section 4.5.4. If a subject in Arm N-I dose level 2d meets criteria for discontinuation of nivolumab or nivolumab and ipilimumab, the subject should discontinue all agents, nivolumab, ipilimumab, and cobimetinib and be taken off the treatment phase of the study entirely.

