The combination of nivolumab and ipilimumab has the potential for increased frequencies of adverse events compared to ipilimumab monotherapy or nivolumab monotherapy. The most common (reported at > 10% incidence) treatment related AEs are fatigue, rash, pruritus, diarrhea, lipase increased, pyrexia, ALT increase, AST increased, amylase increased, and vitiligo. This class of AEs are expected for the combination of nivolumab and ipilimumab based on the known AE profile of each drug alone. In addition, many of the Grade 3-4 adverse events were laboratory in nature (ie, LFTs, lipase, amylase), were without clinical sequelae and have been manageable and reversible following intervention dose delays or with systemic steroid treatment. However, these AEs have the potential to be fatal if not detected early and managed per the established algorithm and fatal AEs have been reported for both ipilimumab and nivolumab monotherapy. As of June 2013, one subject died because of a study treatment related adverse event (toxic epidermal necrolysis, TEN) in the nivolumab + ipilimumab development program. Fatal TEN has previously been reported for ipilimumab monotherapy.

Evaluating nivolumab monotherapy and the combination of nivolumab and ipilimumab in subjects with advanced or metastatic solid tumors for which no standard of care in advanced lines of treatment exists, will potentially generate efficacy signals as a basis for further clinical development in these tumor types.

Across multiple tumors, 3 mg/kg nivolumab as well as 3 mg/kg ipilimumab monotherapy have demonstrated a tolerable AE profile in hundreds, respectively thousands of subjects that appears to be independent of tumor type. The combination of 1 mg/kg nivolumab + 3 mg/kg ipilimumab has demonstrated an acceptable AE profile in melanoma and is currently in Phase 3. The same regimen is currently being studied in RCC and NSCLC. The following safety measures have been employed to ensure safety of the subjects in this current study:

- Intense toxicity monitoring will help to ensure the subjects' safety in Study CA209032, including frequent safety conference calls with investigators and representatives of the sponsor
- A BMS medical safety team (MST) routinely reviews safety signals across the entire nivolumab program, including all ongoing combinations with ipilimumab
- Two stage design used which will stop an individual arm for lack of sufficient activity

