3.1.6 Crossover for Subjects in Arm N

Subjects in Arm N may crossover to Arm N-I if all of the following criteria are met:

- The Safety Evaluation Phase for the N-I regimen has been completed and at least 6 subjects have been exposed to the dose level used for Stage 1 of the N-I regimen. In case Dose Level 2b has been activated and completed the safety assessment, subjects for cross over will be assigned to Dose Level 2 or Dose Level 2b after discussion between the sponsor and investigator taking into consideration previous safety and efficacy signals at these dose levels and the status of the individual subject planned for cross over.
- Subject has further disease progression (investigator-assessed RECIST 1.1-defined progression according to description provided in [Section 4.5.7](#), confirmed at least 4 weeks after the initial tumor assessment showing progression (definition of confirmed progression see [Appendix 3](#))) in the absence of clinical deterioration. For subjects with clear evidence of new or progressing brain metastases a confirmation is not required. These subjects may proceed with brain radiation therapy and, if necessary, with gamma-knife or surgical resection, after having completed the therapy a cross over to Arm N-I can be considered (see [Section 3.4.2.1](#)).
- Subjects with rapidly progressing tumors under nivolumab monotherapy may undergo radiation treatment first before initiation of the cross over after discussion between the sponsor and investigator.
- Subject has not experienced nivolumab related adverse events leading to permanent discontinuation as described in [Section 4.5.5](#).
- Subject is not continuing to derive any clinical benefit from nivolumab single agent therapy as assessed by the investigator which would allow continuation of nivolumab monotherapy (see [Section 4.5.8](#)).
- Subject is not a SCLC patient enrolled based on the Amendment 09 expansion.
- The individual case must be discussed with the medical monitor prior to cross over.

Subjects crossing over to Arm N-I will start treatment at Day 1 Week 1 as described for subjects originally randomized to Arm N-I. Subjects who crossed over and subsequently have an objective response in Arm N-I will not be considered in the decision making for Arm N-I proceeding to Stage 2. Subjects in Arm N-I cannot crossover to Arm N.

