4.5.2 Dose Delay Criteria

Nivolumab and Ipilimumab

These dose delay criteria apply for all drug-related adverse events attributed to nivolumab, ipilimumab, or both. All study drugs must be delayed until treatment can resume (see [Section 4.5.4](#)).

Nivolumab and ipilimumab administration should be delayed for the following:

- Any Grade ≥ 2 non-skin, drug-related adverse event, with the following exceptions:
 - Grade 2 drug-related fatigue or laboratory abnormalities do not require a treatment delay
- Any Grade 3 skin drug-related adverse event
 - Any Grade 3 drug-related laboratory abnormality, with the following exceptions for asymptomatic amylase or lipase, lymphocytopenia, AST, ALT, or total bilirubin:
 - ◆ Grade 3 amylase or lipase abnormalities that are not associated with symptoms or clinical manifestations, or radiographic signs of pancreatitis do not require a dose delay. It is recommended to consult with the BMS Medical Monitor for Grade 3 amylase or lipase abnormalities.
 - ◆ If a subject has a baseline AST, ALT, or total bilirubin that is within normal limits, delay dosing for drug-related Grade ≥ 2 toxicity
 - ◆ If a subject has baseline grade 1 AST, ALT, or total bilirubin elevation, delay dosing for drug-related Grade ≥ 3 toxicity
 - ◆ Grade 3 lymphocytopenia not associated with symptoms or clinical manifestations. It is recommended to consult with the BMS Medical Monitor for Grade 3 lymphocytopenia before treatment continuation.
- Any adverse event, laboratory abnormality, or concurrent illness which, in the judgment of the investigator, warrants delaying the dose of study medication.

Because of the potential for nivolumab- or ipilimumab-related AEs requiring early recognition and prompt intervention, management algorithms have been developed for suspected pulmonary toxicity, GI toxicity, hepatotoxicity, endocrinopathy, skin toxicity, neurological toxicity, and nephrotoxicity.

In order to standardize the management of adverse events for all subjects, treatment management algorithms recommended for utilization in Study CA209032 are included in [Appendix 2](#). Adverse event treatment management algorithms included in the Nivolumab IB or Ipilimumab IB might be considered for individual cases.

Cobimetinib

Dose delay criteria for the management of toxicities of individual subjects taking cobimetinib are summarized in [Section 4.5.3](#) and in the prescribing information.⁵⁷

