APPENDIX 2 MANAGEMENT ALGORITHMS

These general guidelines constitute guidance to the Investigator and may be supplemented by discussions with the Medical Monitor representing the Sponsor. The guidance applies to all immuno-oncology agents and regimens.

A general principle is that differential diagnoses should be diligently evaluated according to standard medical practice. Non-inflammatory etiologies should be considered and appropriately treated.

[figure not shown]
Corticosteroids are a primary therapy for immuno-oncology drug-related adverse events. The oral equivalent of the recommended IV doses may be considered for ambulatory patients with low-grade toxicity. The lower bioavailability of oral corticosteroids should be taken into account when switching to the equivalent dose of oral corticosteroids.

Consultation with a medical or surgical specialist, especially prior to an invasive diagnostic or therapeutic procedure, is recommended.

The frequency and severity of the related adverse events covered by these algorithms will depend on the immuno-oncology agent or regimen being used.

GI Adverse Event Management Algorithm

Rule out non-inflammatory causes. If non-inflammatory cause is identified, treat accordingly and continue I-O therapy. Opiates/narcotics may mask symptoms of perforation. Infliximab should not be used in cases of perforation or sepsis.

[figure not shown]

Patients on IV steroids may be switched to an equivalent dose of oral corticosteroids (e.g. prednisone) at start of tapering or earlier, once sustained clinical improvement is observed. Lower bioavailability of oral corticosteroids should be taken into account when switching to the equivalent dose of oral corticosteroids.

27-Jun-2019

Renal Adverse Event Management Algorithm

Rule out non-inflammatory causes. If non-inflammatory cause, treat accordingly and continue I-O therapy.

[figure not shown]

Patients on IV steroids may be switched to an equivalent dose of oral corticosteroids (e.g. prednisone) at start of tapering or earlier, once sustained clinical improvement is observed. Lower bioavailability of oral corticosteroids should be taken into account when switching to the equivalent dose of oral corticosteroids.

27-Jun-2019

Pulmonary Adverse Event Management Algorithm

Rule out non-inflammatory causes. If non-inflammatory cause, treat accordingly and continue I-O therapy. Evaluate with imaging and pulmonary consultation.

[figure not shown]

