Patients on IV steroids may be switched to an equivalent dose of oral corticosteroids (e.g. prednisone) at start of tapering or earlier, once sustained clinical improvement is observed. Lower bioavailability of oral corticosteroids should be taken into account when switching to the equivalent dose of oral corticosteroids

27-Jun-2019

Hepatic Adverse Event Management Algorithm

Rule out non-inflammatory causes. If non-inflammatory cause, treat accordingly and continue I-O therapy. Consider imaging for obstruction.

[figure not shown]
Patients on IV steroids may be switched to an equivalent dose of oral corticosteroids (e.g. prednisone) at start of tapering or earlier, once sustained clinical improvement is observed. Lower bioavailability of oral corticosteroids should be taken into account when switching to the equivalent dose of oral corticosteroids.

*The recommended starting dose for grade 4 hepatitis is 2 mg/kg/day methylprednisolone IV.

27-Jun-2019

Endocrinopathy Adverse Event Management Algorithm

Rule out non-inflammatory causes. If non-inflammatory cause, treat accordingly and continue I-O therapy. Consider visual field testing, endocrinology consultation, and imaging.

[figure not shown]

Patients on IV steroids may be switched to an equivalent dose of oral corticosteroids (e.g. prednisone) at start of tapering or earlier, once sustained clinical improvement is observed. Lower bioavailability of oral corticosteroids should be taken into account when switching to the equivalent dose of oral corticosteroids.

27-Jun-2019

Skin Adverse Event Management Algorithm

Rule out non-inflammatory causes. If non-inflammatory cause, treat accordingly and continue I-O therapy.

Patients on IV steroids may be switched to an equivalent dose of oral corticosteroids (e.g. prednisone) at start of tapering or earlier, once sustained clinical improvement is observed. Lower bioavailability of oral corticosteroids should be taken into account when switching to the equivalent dose of oral corticosteroids.

[figure not shown]
*Refer to NCI CTCAE v4 for term-specific grading criteria.

^If SJS/TEN is suspected, withhold I-O therapy and refer patient for specialized care for assessment and treatment. If SJS or TEN is diagnosed, permanently discontinue I-O therapy.

27-Jun-2019

Neurological Adverse Event Management Algorithm

[figure not shown]
Rule out non-inflammatory causes. If non-inflammatory cause, treat accordingly and continue I-O therapy.

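### The dose-delay, resumption and stopping rules in Sections 4.5.2, 4.5.4 and 4.5.5 are not reconciled with the Appendix 2 footnote on Stevens-Johnson syndrome and toxic epidermal necrolysis

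*Protocol*

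**What the plan says.** Three sections in the body of the protocol govern drug-related skin events by grade.

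- **4.5.2 (delay):** the skin-specific trigger is "Any Grade 3 skin drug-related adverse event". A final bullet lets the investigator delay for any event that in their judgment calls for it.
- **4.5.4 (resumption):** "Subjects may resume treatment with study drug when the drug-related AE(s) resolve to Grade" 1 or lower, or to the baseline value. The listed exceptions cover fatigue, liver tests, pulmonary toxicity, diarrhoea or colitis, and endocrinopathies. None concerns skin.
- **4.5.5 (discontinuation):** the Grade 3 criterion is "Any Grade 3 non-skin, drug-related adverse event lasting > 7 days", with its own list of exceptions. The Grade 4 criterion is "Any Grade 4 drug-related adverse event or laboratory abnormality, except for the following events which do not require discontinuation", and no skin event is among those exceptions. SJS and TEN are not named. A separate clause stops treatment for any event that the investigator judges too hazardous for dosing to continue.

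Section 4.5.5 also allows ipilimumab alone to be stopped in Arm N-I, with nivolumab going on, when the investigator attributes the event to ipilimumab only. A parallel clause covers dose level 2d.

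Appendix 2, in its algorithms dated 27-Jun-2019, has a footnote to the skin algorithm. It says to withhold immuno-oncology therapy and refer the patient when SJS or TEN is suspected, and then: "If SJS or TEN is diagnosed, permanently discontinue I-O therapy". On its own standing the appendix says: "These general guidelines constitute guidance to the Investigator". Section 4.5.2 describes the algorithms as recommended.

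**The concern.** Two parts of one protocol give different instructions for the same diagnosed event. The body works by grade and by the agent blamed. The appendix works by diagnosis and covers immuno-oncology therapy as a whole. Two sites with identical cases could therefore act differently on re-dosing.

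The event type is not trivial. Section 1.5 reports one treatment-related death in the nivolumab plus ipilimumab programme as of June 2013, and the cause was TEN. It adds that fatal TEN had already been reported with ipilimumab alone.

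Other rules lean on 4.5.5. Crossover from Arm N requires that the "Subject has not experienced nivolumab related adverse events leading to permanent discontinuation", as described in 4.5.5. Re-exposure (3.1.7) and the tolerability criteria (3.1.2) refer to the same section. The main measure of the safety objective in 8.3.2 is the rate of treatment-related events leading to discontinuation in the first 12 weeks. A case that is resumed does not enter that count, and an identical case that is stopped does.

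**Working it through.** No sample size, power or event count is involved, so the check is a comparison of the texts.

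**Step 1: compare by grade.**

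| Case | 4.5.2, 4.5.4, 4.5.5 | Appendix 2 footnote | Do they agree? |
|---|---|---|---|
| SJS/TEN suspected or diagnosed, graded 2 or lower | No skin-specific delay trigger and no grade-based stop; delay or stop only by investigator judgment | Withhold on suspicion, stop on diagnosis | Not assured |
| Diagnosed, Grade 3 | Delay; may resume at Grade 1 or lower or baseline; Grade 3 stop excludes skin; stop by judgment or if the interruption exceeds 6 weeks | Permanent stop | No, unless a stop is made on one of those other grounds |
| Diagnosed, Grade 4 | Permanent discontinuation | Permanent stop | Yes on stopping; see Step 2 on which agent |

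The first row is the least certain. The footnote states no grade, but the algorithm figure is not reproduced in the text available, so the grade box carrying the footnote marker cannot be seen.

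**Step 2: compare by agent.** Where 4.5.5 leads to discontinuation, at Grade 4 or through investigator judgment, attribution to ipilimumab only lets nivolumab continue at 3 mg/kg every 2 weeks. This requires that the resumption criteria are met and the medical monitor has been contacted. The dose level 2d clause likewise lets the remaining drugs go on. Neither clause excepts SJS or TEN. The Appendix 2 footnote stops immuno-oncology therapy without separating the agents, and the appendix says that it covers all such agents and regimens. The texts can therefore diverge even at Grade 4.

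**Step 3: look for a precedence rule.** There is none. Section 4.5.2 brings in the algorithms to standardise management but calls them recommended, and it also lets Investigator Brochure algorithms be considered in individual cases. Nothing ranks the body above the appendix, or the reverse.

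**Step 4: look for clauses that close the gap.** Three help:

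- 3.5 requires a stop when the investigator thinks that continuing is not in the subject's best interest.
- 4.5.5 has its own investigator-judgment clause.
- 4.5.4 and 4.5.5 stop treatment after an interruption of more than 6 weeks, but prolonged steroid tapers for drug-related events are exempt.

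The first two depend on judgment. The appendix instruction follows from the diagnosis alone.

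**Step 5: check both versions.** The document holds Revised Protocol 07D and Revised Protocol 08. The skin rules, the ipilimumab-only clause and the footnote read the same in both. The dose level 2d clause is in 07D only.

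**The case against.** The strongest reply is that an investigator can obey every text at once by stopping treatment, because 3.5 and 4.5.5 both permit it at any grade. Withholding on suspicion likewise fits the judgment bullet of 4.5.2. A specific SJS/TEN instruction can also be read as adding to general grade rules rather than opposing them. This stands in part. It means the conflict is not one that makes compliance impossible, and a reader should not infer that the body re-doses every skin event below Grade 4. It does not remove the gap, because the graded rules alone do not reach the stop that the appendix states. Section 4.5.5 also names uveitis, pneumonitis and colitis at Grade 3 even though it has the judgment clause.

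A reader might also infer that the body outranks the appendix because the appendix calls itself guidance. No passage says so, and 4.5.5 itself is worded as what should be done.

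The downstream effects are limited, and that part of the reply stands:

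- Section 3.1 describes the escalation evaluation in the four original tumour types as already conducted.
- Section 3.1.7 separately bars re-exposure for anyone who has permanently discontinued and is in follow-up.
- Each crossover must be discussed with the medical monitor, and the SCLC expansion is excluded.
- The 12-week measure in 8.3.2 counts discontinuations without citing 4.5.5.

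**Conclusion.** The passages are unreconciled as written. For a diagnosed SJS/TEN event graded 3, the graded rules lead to delay and possible resumption where Appendix 2 leads to a permanent stop. Where 4.5.5 does stop treatment, the ipilimumab-only and dose level 2d clauses can keep nivolumab going where the appendix would not. The outcome then rests on investigator judgment and on which page is read.

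The size cannot be fixed from the documents. They state no grade for SJS or TEN and defer to CTCAE v4, so it is not shown that TEN can be graded below 4. The number of affected cases runs from none, if every case is Grade 4 and not attributed to ipilimumab alone or if investigators always stop all immuno-oncology therapy, up to every diagnosed case graded 3 or lower plus any Grade 4 case attributed to ipilimumab only. It may be very small, and the effect on reported rates is likely to be small too.

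The skin-event rates in Table 1.1.8.2-3 (69.8% any grade, 3.8% Grade 3-4 on the combination) might be taken as a measure of the problem. They are not: the terms listed there are pruritus and rash, and they give no SJS/TEN frequency. The reason to act is the seriousness of the event type and the low cost of clearing it up.

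**What to change.** Reconcile 4.5.2, 4.5.4 and 4.5.5, including the ipilimumab-only and dose level 2d clauses, with the SJS/TEN footnote of Appendix 2, so that one rule governs suspected and diagnosed cases. State which text prevails when a 4.5 section and an Appendix 2 algorithm differ. Make the references to 4.5.5 in 3.1.6 (crossover), 3.1.7 (re-exposure) and any part of 3.1.2 (tolerability) still in use follow the reconciled rule. Which clinical rule to adopt is the sponsor's decision, and this review takes no position on it.

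The cost is a few lines at the next amendment, in both protocol versions where both remain in force. It adds no procedures, visits or subjects.

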Liver Laboratory Abnormalities and Hepatotoxicity	
First occurrence Grade 4	Withhold COTELLIC for up to 4 weeks. 
 If improved to Grade 0 or 1, then resume at the next lower dose level. If not improved to Grade 0 or 1 within 4 weeks, permanently discontinue
Recurrent Grade 4	Permanently discontinue COTELLIC.
Rhabdomyolysis and Creatine Phosphokinase (CPK) elevations	

 Grade 4 CPK elevation Any CPK elevation and myalgia 	Withhold COTELLIC for up to 4 weeks. 
 If improved to Grade 3 or lower, resume at the next lower dose level. If not improved within 4 weeks, permanently discontinue.
Photosensitivity	
Grade 2 (intolerable), Grade 3 or Grade 4	Withhold COTELLIC for up to 4 weeks. 
 If improved to Grade 0 or 1, resume at the next lower dose level. If not improved within 4 weeks, permanently discontinue.
Other	

 Grade 2 (intolerable) adverse reactions Any Grade 3 adverse reactions 	Withhold COTELLIC for up to 4 weeks. 
 If improved to Grade 0 or 1, resume at the next lower dose level. If not improved within 4 weeks, permanently discontinue.
First occurrence of any Grade 4 adverse reaction	
 Withhold COTELLIC until adverse reaction improves to Grade 0 or 1. Then resume at the next lower dose level, OR Permanently discontinue
Recurrent Grade 4 adverse reaction	Permanently discontinue COTELLIC.

^a NCI CTCAE v 4.0

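### Dose level 2d: after a cobimetinib-only attribution the antibodies may go on without the documentation and prior medical monitor contact that an ipilimumab-only attribution requires, and the continuation rule is worded two ways

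*Protocol*

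**What the plan says.** Dose level 2d exists only in the protocol version with the additional pancreatic cancer cohort (Revised Protocol 07D). Four parts of that version govern what happens to nivolumab and ipilimumab when a toxicity is blamed on cobimetinib.

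- **Section 4.5.5, dose level 2d paragraph.** If the investigator attributes the event to ipilimumab or cobimetinib only, "treatment with the agent causing the AE alone may be permanently discontinued and treatment with the remaining drugs will continue". The following sentence reads: "Treatment with the remaining drugs may only be resumed when the subject meets criteria to resume treatment according to section 4.5.4".
- **Section 4.5.5, Arm N-I paragraph on ipilimumab-only events.** Nivolumab is delayed until section 4.5.4 is met, the relationship to ipilimumab should be well documented in the source, and "the BMS medical monitor needs to be contacted prior to continuation with nivolumab therapy".
- **Section 4.5.3, Table 4.5.3-1.** For any Grade 3 reaction not covered by a specific row, the instruction is "Withhold COTELLIC for up to 4 weeks". For a first Grade 4 reaction, cobimetinib is withheld to Grade 0 or 1 or stopped. The table does not mention the antibodies.
- **Section 4.5.2.** "These dose delay criteria apply for all drug-related adverse events attributed to nivolumab, ipilimumab, or both". The discontinuation criteria in section 4.5.5 carry the same limit.

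Section 4.5.4 sets the bar for restarting: "Drug-related pulmonary toxicity, diarrhea, or colitis must have resolved to baseline before treatment is resumed".

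**The concern.** In this arm a great deal hangs on one attribution. Grade 3 diarrhea or colitis attributed to the antibodies requires discontinuation whatever its duration. In dose level 2d, meeting the criteria for stopping nivolumab takes the patient off all three agents. The same event attributed to cobimetinib only can leave both antibodies running.

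The attribution is also hard to make. Section 1.1.7 lists diarrhea among the most common cobimetinib toxicities, including at Grade 3 or higher. Section 1.5 lists it among the treatment-related events seen in more than 10% of patients on nivolumab plus ipilimumab. Section 1.1.4 names it among the most common effects of cobimetinib given with an anti-PD-L1 antibody.

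If the cobimetinib-only call is wrong, a patient with antibody-related colitis can receive more nivolumab, and possibly ipilimumab, before it resolves. The protocol already recognises this kind of risk for ipilimumab-only calls and attaches a check to them, but it does not carry that check over to cobimetinib. Separately, a site reading the dose level 2d paragraph cannot tell for certain whether the antibodies go straight on or wait.

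**Working it through.** The plan states no figure to reproduce here; the check is mainly a comparison of the rules.

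**Step 1: cobimetinib permanently stopped.** The first sentence of the 2d paragraph says the other drugs go on; the second admits them only under section 4.5.4. There are two readings.

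- *Restrictive:* the antibodies wait until section 4.5.4 is met, which for diarrhea or colitis means a return to baseline. The parallel ipilimumab-only paragraph, which delays nivolumab until section 4.5.4 is met, supports this.
- *Lenient:* the second sentence applies only to a drug that had already been delayed for some other reason. The wording does not exclude this.

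**Step 2: cobimetinib only withheld.** Table 4.5.3-1 is silent on the antibodies. The delay criteria (4.5.2) and discontinuation criteria (4.5.5) are confined to events attributed to nivolumab, ipilimumab or both. A cobimetinib-only event therefore triggers no mandatory antibody delay.

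**Step 3: safeguards compared.**

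| Attribution and action | Antibody wait required | Source documentation of the attribution | Monitor contact before the antibodies go on |
|---|---|---|---|
| Ipilimumab only, ipilimumab stopped | Yes, to section 4.5.4 | Yes | Yes |
| Cobimetinib only, cobimetinib stopped | Depends on the reading in step 1 | Not stated | Not stated |
| Cobimetinib only, cobimetinib withheld | No | Not stated | Not stated |

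**Step 4: what else protects the patient.** The investigator may delay dosing for any event (4.5.2). Treatment must stop where an event, in the investigator's judgment, "presents a substantial clinical risk to the subject with continued nivolumab, ipilimumab, or cobimetinib dosing" (4.5.5; section 3.5 is similar). The gastrointestinal algorithm in Appendix 2 tells the investigator to rule out non-inflammatory causes. Section 3.1.1 gives daily Medical Monitor review, a scheduled review after 12 patients, and regular investigator calls. These are discretion, guidance or general oversight. None is a required check tied to the next antibody dose.

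**Step 5: exposure per affected patient.** Inputs: nivolumab every 14 days and ipilimumab every 42 days (Table 5.1-6); maximum Grade 3 hold of 28 days (Table 4.5.3-1).

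- Nivolumab doses falling in a full hold: 28 / 14 = 2.
- Ipilimumab doses falling in a full hold: 28 / 42 = 0.67 on average, so 0 or 1 depending on timing.

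**The case against.** The strongest reply is that existing oversight suffices. The Medical Monitor looks at this cohort daily, far more often than the antibodies are given; the investigator may delay at will; and Appendix 2 speaks directly to telling inflammatory from other diarrhea. That lowers the risk and is why the point is minor. It does not explain why an ipilimumab-only call needs contact before dosing and a cobimetinib-only call does not.

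A reader might infer more than the text supports, in four ways.

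- *That stopping cobimetinib holds the antibodies while the milder step of withholding it lets them run.* This is true only on the restrictive reading in step 1. The two steps are also mostly sequential: for Grade 3 reactions in the general row, the table withholds first and stops only if there is no improvement within 4 weeks. The 3-day dosing window in Table 5.1-6 is a scheduling limit, not an order to dose through toxicity; section 3.1.12 allows delay for toxicity.
- *That an antibody delay should be mandatory whenever cobimetinib is withheld.* Appendix 2 says to continue immunotherapy once a non-inflammatory cause is identified, and a forced delay would contradict it. It could also end antibody treatment. A last nivolumab dose 14 days before the event plus a 28-day hold is 14 + 28 = 42 days, exactly the 6-week limit, or 17 + 28 = 45 days if the next dose was already 3 days late. The exceptions to that limit (steroid tapers and non-drug-related reasons) do not clearly cover cobimetinib diarrhea.
- *That the same gap exists for AST or ALT above 8 times the upper limit of normal.* Table 4.5.3-1 has its own liver row, which starts at Grade 4, so the general Grade 3 hold does not carry over.
- *That a number of affected patients can be projected.* No misattribution rate or cobimetinib Grade 3 diarrhea rate is given. The nivolumab monotherapy figure in Table 1.1.8.2-1 (3 Grade 3-4 gastrointestinal events in 306) comes entirely from the 10 mg/kg group, with 0 of 54 at the 3 mg/kg used here.

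**Conclusion.** The point holds as a minor, inexpensive improvement confined to dose level 2d. Two things are established from the text. First, the documentation and prior monitor contact required after an ipilimumab-only attribution are not extended to a cobimetinib-only attribution, whether cobimetinib is withheld or stopped. Second, the dose level 2d paragraph gives two instructions on the remaining drugs that do not agree.

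The size is limited: one arm of about 30 patients and an unknown number of events. For each full 4-week hold, up to two nivolumab doses and one ipilimumab dose could be given without a required check. The grade-specific Appendix 2 flowchart is not reproduced in the text at hand, so the conclusion rests on that appendix being guidance, as it describes itself, rather than on what the flowchart says about holding treatment.

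The statements that cobimetinib's toxicity does not overlap with the antibodies' (Synopsis, and sections 1.1.7, 1.5 and 3.1.1) sit badly with the protocol's own lists of common events. Correcting them is editorial.

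**What to change.** In the dose level 2d paragraph of section 4.5.5:

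1. Replace *will continue* with *may continue once the criteria in section 4.5.4 are met*.
2. Add: *For Grade 3 or higher diarrhea or colitis attributed to cobimetinib only, whether cobimetinib is withheld or discontinued, the attribution must be documented in the source documents and the BMS medical monitor contacted before the next nivolumab or ipilimumab dose.*

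Optionally, amend the four non-overlap statements to acknowledge diarrhea as shared.

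The cost is about one monitor contact and one source note per event, with no extra patients or tests. The first change spells out the wait that the paragraph's second sentence already appears to impose after a permanent stop. If the sponsor meant the lenient reading, this would be a real change on that path and should be decided as such. Neither change forces an antibody delay while cobimetinib is only withheld; that stays with the investigator, now after a conversation with the monitor.
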